Study Title: The Effect of Play on Social and Motor Skills of Children With ASD

NCT #: NCT04258254

Date: 06/01/2020

Study Protocol

Participants

45 children with ASD aged between 5 and 15 years were recruited through fliers distributed to local schools, ASD services, advocacy groups, as well as Simons Powering Autism Research (SPARK) participant-research matching service (<https://www.sfari.org/resource/spark/>). We interviewed the potential participants to gather their demographic information (i.e., age, sex, ethnicity), and to confirm their eligibility for participation. Children were included in the study if they had formal ASD diagnoses that were confirmed through a school record (e.g., school psychologist record confirming an ASD diagnosis) and/or an Individualized Education Plan for ASD-related services or a medical or neuropsychological record from a psychiatrist or clinical psychologist using the Autism Diagnostic Observation Schedule (ADOS) and/or Autism Diagnostic Interview-Revised (ADI-R) measures. We additionally used the Social Communication Questionnaire (SCQ) as a screener for ASD symptoms (Rutter et al., 2003). Children were excluded if they have limited comprehension of one-step simple instruction and/or could not complete the pretests due to behavioral issues. Parents of the children completed the Vineland Adaptive Behavioral Scales-2nd edition (VABS; Sparrow et al., 2005), and the Social Responsive Scale questionnaire (SRS; Constantino et al., 2000) to assess the child's adaptive functions and social responsiveness. Following enrollment, children were matched on age, sex, and level of functioning then randomly allocated to the 3 intervention arms. The study procedures were carried out according to the Declaration of Helsinki and were approved by the University of Delaware Institutional Review Board (UD IRB, Study Approval #: 1539736-5). Written informed consent of study participation was obtained from the parent, and a written/verbal assent was obtained from the participating children.

Experimental Procedures

This study includes 3 pretests, 3 posttests, and 16 training sessions conducted over 10 weeks. Eight weeks later a follow-up test was also completed. Specifically, the pretests and posttests were conducted during the first and the last week of the study, while the training sessions were provided during the intermediate 8

weeks (2 sessions per week). After pretests, the children were matched age, sex, and level of functioning and then randomized into the 3 groups. A parent orientation was conducted in-person/ through zoom before the training period to introduce the training activities and intervention strategies. Each training session lasted about one hour. All sessions were video recorded for further behavioral coding. The current study was conducted in the midst of the COVID-19 pandemic (between 2019 and 2022). Due to the initial close down and the later restriction of face-to-face (F2F) interaction, we decided to be more pragmatic and used a hybrid clinical trial delivery model (Bhat et al., 2021; Cleffi et al., 2022; Srinivasan et al., 2021; Su et al., 2021). The participating families chose between an F2F or a Telehealth (TH) training delivery method based on their convenience and comfort level of social interactions during the pandemic.

Training Protocols

For each intervention arm, Applied Behavior Analysis (ABA), Picture Exchange Communication System (PECS), TEACCH, and motor learning principles were used to provide structure, reinforcement, and free time for exploration. Specifically, visual, verbal, manual prompts/assistance, positive reinforcements were given throughout the intervention, and the child was encouraged to choose from a set of actions or improvise their own movement patterns. We also used a picture schedule to explain the order of tasks and to provide more structure to the session. During the training session, people sat/stood in a triad involving the child, expert trainer, and an adult model/parent was used. The expert trainer guided the child through the training-specific activities, while the model/parent assisted and acted as a buddy to provide visual model/assistance for the children. For the F2F intervention delivery format, a trained undergraduate student acted as the model, while for the TH format, the parents were trained to aid during the intervention. Both, undergraduate students and parents were provided in-person/Zoom trainings to explain the training goals, intervention principles, and the main activities according to the intervention types. The key ingredients for the multimodal group included engaging in interpersonal synchrony and multi-limb, whole-body movements performed to music, while the general movement group received multi-limb, whole-body movements based in exercise and games; whereas the seated play, control group focused on reading and fine motor activities.

To ensure training fidelity, a student coder randomly chose and coded one early (session 1-5) and one late session (session 12-16) for each child using a behavior checklist assessing trainer's and the model's behaviors. Specifically, the coder evaluated: A) the accuracy of completing the critical components of the training activities B) Trainer and model's behaviors including instructions, prompts, positive reinforcement/praise, body movements (clarity, energy), voice, affect (smile and expressivity), scored on a 5-point Likert score (1 indicates poor quality and 5 indicates high quality), and C) child's compliance with the training activities, also scored on a 5-point Likert score.

Testing Protocol

Trained testers assessed the training-related changes in motor performance using standardized during each test visit. For the standardized tests, we used the Bruininks-Oseretsky Test of Motor Proficiency (BOT-2) to assess children's gross and fine motor proficiency (Bruininks et al., 2005), a 2-Minute Walk Test (2MWT) to assess their endurance (Bohannon et al., 2018), and the bilateral motor coordination subtests of the Sensory Integration and Praxis Tests (SIPT) to access their praxis performance (Ayres, 1988). Parents also completed the Developmental Coordination Disorder Questionnaire (DCD-Q; Schoemaker et al., 2006) at each test visit, and both parents and the children filled out exit questionnaires to provide feedback on the feasibility, acceptability, and benefits of the interventions

Standardized Tests

Bruininks-Oseretsky Test of Motor Proficiency (BOT-2): BOT-2 is a valid and reliable assessment that targets 4 motor area composites with 8 subscales, including a) Fine Manual Control area, consisting of Fine Motor Precision, Fine Motor Integration subscales; b) Manual Coordination, consisting of Manual Dexterity and Upper-limb Coordination subscales; c) Body Coordination, consisting of Bilateral Coordination and Balance Subscales; and d) Strength and Agility, consisting of Running Speed and Agility and Strength subscales. The standard scores of the four motor areas were used to assess the training-related changes in motor performance.

Two Minute Walk Test (2MWT)

2MWT is a standardized measure of endurance. The child was asked to walk as fast as they can (without running) around 2 cones placed 50-feet apart for 2 minutes. The total distance the child walked in the 2-minute period was used to assess the training-related changes in endurance.

Sensory Integration and Praxis Tests (SIPT): We used the postural praxis and bilateral motor coordination subtests of the Sensory Integration and Praxis Tests (SIPT-PP and SIPT-BMC) to evaluate the praxis and sensory integration performance in children with ASD (Ayres, 1988). During the SIPT-PP, the tester sat across the children and performed 17 novel postures that involved fingers and upper/lower limb movements. An error was counted if the children posed with insufficient/exaggerated joint angles, incorrect joint and hand orientation, or using the wrong side of the body. Similarly, during the SIPT-BMC test, the tester sat across the children and performed 22 rhythmic action sequences involving hand-tapping, foot-stomping, and foot-tapping. The children were asked to repeat the movement sequences back to the tester. An error was counted if the child paused in between the movement sequence, couldn't pick up the rhythm, moved too fast or too slow, or failed to perform the right movement sequences. The number of errors the children made during the SIPT-PP and SIPT-BMC tests were used to monitor the training-related changes in praxis performance.

Executive functioning (EF) Task

During the EF task, we will use e-versions of variations of the Flanker test to assess the inhibition control and cognitive shifting elements of EF. There will be 2 conditions in the Flanker task, including: a) Congruent: Five fishes facing in the same direction (left or right) will be presented, and the child will be asked to raise the left or right index finger depending on the direction in which all the fishes are facing, b) Incongruent: the child will be presented with 4 fishes facing the same direction while the center fish will be facing in the opposite direction. Children will be asked to point to the left or right index finger depending on the direction of the center fish.

Drumming Synchrony Task

During the drumming synchrony task, children will be seated with a drum placed on the table in front of them. There will be 3 conditions: a) Music: the child will be asked to drum in order to match up to rhythmic beats played aloud in the background, b) Social: the child will sit face to face with an adult and be asked to match up to the movements of the adult. C) Virtual Social: the child will be seated facing a laptop screen and drum with a virtual partner through zoom conferencing. Both the child and the virtual partner will drum to rhythmic beats played aloud in the background.

Parent reported motor outcome using the Developmental Coordination Disorder Questionnaire (DCD-Q)

DCD-Q is a parent questionnaire to screen for developmental coordination disorder in children. Specifically, it screens for the child's performance in three components, Control during movement (motor control while the child is moving or the target object is in motion, ex: catching, throwing), Fine motor/Handwriting (fine motor skills, ex: writing fast and legibly), and General coordination (motor planning/learning, ex: like sports and learn new skills).

Children's survey feedback

Upon finishing all training sessions, each child answered 3 questions to provide feedback on their training experience. The questions include: A) Did you enjoy the activities we did? B) Did you find the activities easy or hard, C) Will you practice similar activities on your own or with mom/dad? Each question was answered with a picture-assisted 5-point Likert score (5- definitely yes/ very easy 😊; 4- yes/easy 😃; 3- maybe, neither too easy nor too hard 😐; 2- not so much/hard 😔; 1- not at all/very hard 😞).

Study Title: The Effect of Play on Social and Motor Skills of Children With ASD

NCT #: NCT04258254

Date: 06/01/2020

Statistical Plan

Outcome measures will be obtained at the pretest and posttest. The BOT standardized motor test offers a fine-motor (precision+integration), gross motor coordination, agility and strength scores. The SIPT standardized praxis subtests provides praxis errors. t-tests or Repeated Measures ANOVA will be used to compare scores between post and pretests.

Post-intervention, the multimodal group will show improvements in the standard motor coordination variables, compared to their own baseline and compared to the control group. Specifically, we expect to see improved gross motor scores, fewer praxis errors as well as greater spontaneous verbalization in the multimodal group compared to the general movement or control group. In terms of fNIRS activation data, we expect greater multiregional activation in the multimodal group during the post-test compared to their own baseline. We expect fewer changes in activation or more localized activation in the general movement or control group.

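### The SAP expects the multimodal arm to outperform the other two arms, but its only analysis sentence compares posttest with pretest and names no arm factor or arm contrast

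*SAP*

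**What the plan says.** The Statistical Plan contains one sentence that names a test: "t-tests or Repeated Measures ANOVA will be used to compare scores between post and pretests". The comparison it describes is between time points.

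The next paragraph of the SAP states what the trial should show. It expects that "the multimodal group will show improvements in the standard motor coordination variables, compared to their own baseline and compared to the control group". It then expects better gross motor scores, praxis errors and spontaneous verbalization "in the multimodal group compared to the general movement or control group". For brain activation it expects a rise from baseline in multimodal, and adds: "We expect fewer changes in activation or more localized activation in the general movement or control group".

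The protocol (Participants) gives the design: "45 children with ASD aged between 5 and 15 years were recruited", and "children were matched on age, sex, and level of functioning then randomly allocated to the 3 intervention arms". Its testing sections refer to changes related to training and give no analysis method.

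**The concern.** The hypotheses are about differences between arms; the named comparison is within arms over time. A post-versus-pre t-test has no arm term. A repeated-measures ANOVA may have one, but the SAP does not say that it will. Even with arm in the model, three arms leave open which contrast answers the question.

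This matters because a gain common to all arms is plausible from the design. Under Training Protocols, "For each intervention arm, Applied Behavior Analysis (ABA), Picture Exchange Communication System (PECS), TEACCH, and motor learning principles were used". Multimodal and general movement also share multi-limb, whole-body activity. Pretests fall in the first week and posttests in the last week of a 10-week study, so the same tasks are repeated about 9 to 10 weeks apart and practice gains are possible. Maturation could add to raw measures such as SIPT error counts. It should add less to BOT-2 standard scores if these are age-normed, which is an assumption.

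A within-arm test credits all of this to whichever arm is tested. Noting significance in one arm and its absence in another does not test the difference between them. Neither gives an estimate, confidence interval or p-value for the effect of allocation.

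**Working it through.** **Setting the text side by side**

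| SAP expectation | Test named for it |
|---|---|
| Multimodal against its own baseline | Post versus pre, by t-test or repeated-measures ANOVA |
| Multimodal against control, motor variables | None stated |
| Multimodal against general movement or control: gross motor, praxis, verbalization | None stated |
| Fewer or more localized activation changes in the other arms | None stated |

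The documents give no alpha, power, effect size or sample-size calculation, so there is no planned figure to reproduce. What follows only illustrates what the gap could cost.

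**Inputs.** From the protocol: 45 recruited, 3 arms. Assumed: equal split (45/3 = 15 per arm), two-sided 5%, normal scores, independent arms, the same true gain g (in SD of the score) in every arm, and pre-post correlation r of 0.6 to 0.8.

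**Formulas.** Standardised change: dz = g/√(2(1−r)). A paired t-test on n children has n−1 degrees of freedom and noncentrality dz√n. Let p be the chance of significant improvement and q the chance of significant worsening. The misleading pattern (multimodal significantly improved, control not significant) has probability p(1−p−q).

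**Worked cell.** g = 0.5, r = 0.6: dz = 0.5/√0.8 = 0.559; noncentrality 0.559 × √15 = 2.165; p = 0.522; q is negligible; pattern = 0.522 × 0.478 = 0.250.

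**Chance of the misleading pattern, 15 per arm, no true arm difference**

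| Shared gain (SD) | r = 0.6 | r = 0.7 | r = 0.8 |
|---|---|---|---|
| 0.1 | 0.056 | 0.063 | 0.075 |
| 0.2 | 0.109 | 0.129 | 0.164 |
| 0.3 | 0.175 | 0.205 | 0.240 |
| 0.5 | 0.250 | 0.230 | 0.152 |
| 0.8 | 0.093 | 0.038 | 0.005 |
| 1.0 | 0.019 | 0.004 | <0.001 |

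With 12 or 18 per arm, the range for gains of 0.1 to 0.5 SD is 5% to 25%. The decline at larger gains depends on arm size. With 12 per arm, g = 0.8 and r = 0.6, p = 0.805 and the pattern is 0.805 × 0.195 = 0.157.

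**Direct arm contrast.** Comparing mean change between multimodal and control with a two-sample t-test gave a simulated two-sided false-positive rate of 4.9% to 5.1% when the true gains were equal. Two such contrasts sharing the multimodal arm, each at an unadjusted 5%, gave at least one false positive in about 9% of simulated trials. Two independent tests would give 1 − 0.95² = 9.75%.

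**The case against.** The best defence is that the SAP is under-specified, not contradictory. Its analysis sentence is followed directly by expectations relative to the other arms. Repeated-measures ANOVA routinely takes arm as a between-subject factor, and t-tests can compare change between arms. A reader might infer that the sponsor planned only within-arm tests; the documents do not support that, because the hypotheses show that a between-arm comparison is intended. What survives is narrower: the method for that comparison, and its contrasts, are not written down. It also follows that ANCOVA is not the only acceptable remedy.

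The illustration has limits too.

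- For shared gains of 0.1 to 0.5 SD, the multimodal paired test is significant for improvement in 6% to 81% of trials. A reader might take this as an error rate. It is power to detect a gain that really occurred, and it misleads only if read as an arm effect.
- The pattern probability is close to p(1−p), so it cannot exceed about 25% whatever the data, and it falls away for large gains.
- The pattern counts improvement only, whereas the 5% for the direct contrast is two-sided. The like-for-like figure is about 2.5%, so the comparison understates the gap.
- A reader might infer that matching makes a direct contrast conservative. That holds only if matching correlates the change scores across arms. If it correlates only the stable level (0.3 or 0.5, with r = 0.7), the contrast stays near 5% and the pattern at about 20% to 23%. The documents do not say which applies.

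**Conclusion.** The concern holds as a gap in specification. Neither document names a test of the trial's own randomised hypothesis, and an analyst could apply the stated method without producing one. This conclusion rests on the text alone.

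The size is illustrative: about 6% to 25% for the misleading pattern at shared gains of 0.1 to 0.5 SD and under 10% at 0.8 SD or more, against about 5% per direct contrast. These figures assume 15 per arm, two-sided 5%, independent arms and r of 0.6 to 0.8, none of which the documents state. They concern one outcome. The gap should be closed before any claim is made about multimodal relative to another arm.

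**What to change.** Replace the analysis sentence with text to this effect:

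- Each outcome with a defined pretest and posttest score is compared between allocated arms. Use either ANCOVA of the posttest with arm as factor and pretest, age and sex as covariates, or repeated-measures ANOVA with arm as between-subject factor and named group-by-time contrasts.
- The key contrast is multimodal minus control; the second is multimodal minus general movement. Test them in that fixed order or with a multiplicity adjustment. Report each with a 95% confidence interval.
- Within-arm changes are descriptive only.

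Level of functioning, also used for matching, can be added as a covariate once its measure is named. For fNIRS activation and spontaneous verbalization, the protocol text supplied defines no score. Apply the same contrast only to a summary score that has been defined; otherwise report those results as descriptive.

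The protocol says the study ran between 2019 and 2022. If outcomes have already been seen, date the change and disclose that the contrasts were not prespecified.

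The cost is SAP wording and slightly more analysis. Pretest and posttest motor scores, arm, age and sex are already collected. Naming the contrast does not add precision: on change scores with 15 per arm, 80% power at two-sided 5% needs a difference of about 1.06 SD of change, so intervals may be wide.

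### The SAP expects differences between arms but names only post-versus-pre tests; specify a direct between-arm comparison adjusted for the pretest

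*SAP*

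**What the plan says.** The SAP's Statistical Plan makes two kinds of prediction for the multimodal arm. One is improvement in motor coordination "compared to their own baseline and compared to the control group", which combines a within-arm and a between-arm claim. The other is better gross motor scores, fewer praxis errors and "greater spontaneous verbalization in the multimodal group compared to the general movement or control group", which is purely between arms.

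The only analysis named is: "t-tests or Repeated Measures ANOVA will be used to compare scores between post and pretests". It mentions no arm factor, arm-by-time term, between-arm contrast or covariate.

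The protocol does not fill the gap. Under Standardized Tests it says of the BOT-2: "The standard scores of the four motor areas were used to assess the training-related changes in motor performance". That describes a measure of change, not a comparison of arms.

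Two other statements bear on the remedy. The SAP says: "Outcome measures will be obtained at the pretest and posttest". The protocol's Experimental Procedures place matching and randomisation after the pretests: "the children were matched age, sex, and level of functioning and then randomized into the 3 groups". The pretest is therefore available as a covariate fixed before allocation.

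**The concern.** A post-versus-pre test answers whether an arm changed. It does not answer whether one arm changed more than another. The SAP makes both claims and gives a method only for the first, so the reader must guess how the second will be tested. There are two plausible readings:

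- **Separate tests within each arm.** The between-arm hypothesis is then never tested. A significant change in the multimodal arm beside a non-significant one in the control arm could be taken as a difference, although that pattern arises readily when both arms change equally.
- **Change scores compared between arms, or an arm-by-time term.** This is a valid test. It subtracts the whole pretest instead of weighting it by how well it predicts the posttest, and so usually gives away precision.

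With 45 children in three arms, precision is scarce.

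**Working it through.** The plan gives no sample-size or power figure, so there is nothing to reproduce.

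**Inputs from the documents.** 45 children and 3 arms (protocol, Participants); outcomes at pretest and posttest (SAP).

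**Assumed, because the documents do not state them.** Equal allocation (45/3 = 15 per arm), full retention, a true difference of 0.75 SD, two-sided 5%, equal SDs at both times, and a pre-post correlation r from 0.5 to 0.9.

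**Reading 1: separate within-arm tests.** Suppose two arms change equally and each within-arm test has power p. The chance that the multimodal arm is significant and the control arm is not is p(1 − p):

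- p = 0.3: 0.3 × 0.7 = 21%
- p = 0.5: 0.5 × 0.5 = 25%
- p = 0.8: 0.8 × 0.2 = 16%

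**Reading 2: a direct comparison of change.** With two time points, the arm-by-time test is the change-score test. Per-child variances, in SD² units:

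- change score: 2(1 − r)
- ANCOVA on pretest: 1 − r²
- ratio of ANCOVA to change score: (1 + r)/2

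That ratio ignores the cost of estimating the pretest slope. With N = 45, 3 arms and one covariate, the cost factor is 1 + 1/(45 − 3 − 1 − 1) = 1.025. The net ratio is 1.025(1 + r)/2:

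- r = 0.5: 0.77
- r = 0.7: 0.87
- r = 0.8: 0.92
- r = 0.9: 0.97

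It reaches 1 at r = 2/1.025 − 1 = 0.95. At r = 0.7, change scores on 45 children are worth ANCOVA on about 45 × 0.87 = 39.

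**Power.** The standard error of a two-arm contrast is √(2 × variance/15). Error degrees of freedom are 42 for change scores and 41 for ANCOVA, with critical t 2.018 and 2.020. At r = 0.7:

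- Change score: variance 2 × 0.3 = 0.60; SE = √(1.20/15) = 0.283; half-width 2.018 × 0.283 = 0.57 SD; noncentrality 0.75/0.283 = 2.65; power 73.6%.
- ANCOVA: variance 0.51 × 1.025 = 0.523; SE = √(1.0455/15) = 0.264; half-width 2.020 × 0.264 = 0.53 SD; noncentrality 0.75/0.264 = 2.84; power 79.2%.

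| r | Change score | Pretest ANCOVA |
|---|---|---|
| 0.5 | 51.9% | 62.8% |
| 0.7 | 73.6% | 79.2% |
| 0.8 | 88.7% | 91.0% |
| 0.9 | 99.4% | 99.5% |

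Power is near its ceiling in the last row. With a 0.5 SD difference at r = 0.9 the same formulas give 84.9% and 85.8%, so the gain there is about 1 point.

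**Adding age, sex and functioning.** In a simulation of exactly matched triplets at r = 0.7 and 0.75 SD, with within-set correlation from 0.1 to 0.4, pretest ANCOVA had about 80% power and the four-covariate model 80% to 84%. The extra gain is thus 0 to 3 points.

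If the three factors predict nothing beyond the pretest and matching gave no balance, the cost factor for four covariates is 1 + 4/(45 − 3 − 4 − 1) = 1.108. The variance ratio to change scores is then 0.85 × 1.108 = 0.94 at r = 0.7, 0.90 × 1.108 = 1.00 at r = 0.8 and 0.95 × 1.108 = 1.05 at r = 0.9. In that corner the larger model ties and then loses. A simulation at r = 0.9 and 0.5 SD agrees: 85.0% for change scores, 86.2% for pretest-only ANCOVA, 83.1% for the four-covariate model.

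**The case against.** The strongest reply is that repeated measures ANOVA in a three-arm trial with stated between-arm hypotheses naturally means an arm-by-time test. That test is valid, so what remains is a preference for efficiency, and its size rests on a correlation, effect size, retention and allocation that the documents do not give. Much of this stands. On that reading there is no bias and no excess of false positives, and at r = 0.8 the gain is only about 2 points. But the SAP does not say that arm by time is intended, and its wording fits separate within-arm t-tests equally well.

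Three stronger readings are tempting, and the documents do not support them:

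- **That the planned analysis is invalid, or conversely that only precision is at stake.** Either would require knowing how arms will be compared, which the SAP leaves open.
- **That ANCOVA always wins.** At N = 45 the slope has a cost, and break-even is near r = 0.95.
- **That the matching factors must be in the model because allocation used them ("Following enrollment, children were matched on age, sex, and level of functioning then randomly allocated to the 3 intervention arms").** Their added gain is small and can turn negative. The protocol does not say which measure defined level of functioning, or that a score was used. The Vineland and SRS questionnaires were completed "to assess the child's adaptive functions and social responsiveness", but neither is tied to the matching. Choosing a measure after outcomes are known would be post hoc. BOT-2 is analysed as standard scores; if these are age-referenced, which the documents do not say, age may add little.

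The scope is also limited. The power figures assume a continuous score with constant variance and do not cover the SIPT error counts. The protocol describes no pretest measure of spontaneous verbalization.

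**Conclusion.** The gap is real: the SAP makes between-arm claims without assigning an analysis to them. The consequence depends on what is intended. Separate within-arm tests would leave the claim untested, with a misleading split in significance 16% to 25% of the time when two arms change equally and within-arm power is 30% to 80%. A change-score or arm-by-time comparison would be valid but usually less precise. Under the assumptions above, the loss against pretest ANCOVA is about 11 power points at r = 0.5, 6 at r = 0.7 and 2 at r = 0.8, and is negligible from about 0.9. Most of the dependable gain comes from the pretest; the matching factors are secondary. This is an improvement available at almost no cost, not a finding that the trial's results would be wrong.

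**What to change.** Add to the SAP wording along these lines:

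> Each between-arm comparison of a continuous outcome measured at pretest and posttest will use an ANCOVA of the posttest score on arm, with all three arms in one model, adjusted for the pretest score. Claims of a difference between arms will rest on the contrasts multimodal versus control and multimodal versus general movement.

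Keep the within-arm pre-post comparisons for the own-baseline hypothesis.

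Age, sex and the functioning measure used for matching may be added as pre-specified covariates if that measure can be identified, or used in a sensitivity analysis. They are not essential.

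For spontaneous verbalization the model applies only if a pretest value exists. For the SIPT error counts, the SAP should say whether they are treated as continuous; no gain has been shown for them here.

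The cost is a few lines of text and one error degree of freedom (42 to 41). No new data are needed.

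### The planned pre-post comparison does not condition on the pretest and uses only children with both scores, so it is biased if posttest loss differs by arm and depends on the pretest

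*SAP*

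**What the plan says.** The SAP (Statistical Plan) sets two time points: "Outcome measures will be obtained at the pretest and posttest". Its one sentence on method is "t-tests or Repeated Measures ANOVA will be used to compare scores between post and pretests". It expects the multimodal group to improve "compared to their own baseline and compared to the control group", and it also predicts an advantage over the general movement group. The conclusions sought are therefore between arms as well as within them.

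The protocol (Participants) states that "45 children with ASD aged between 5 and 15 years were recruited" and were "then randomly allocated to the 3 intervention arms". Under Experimental Procedures the order is explicit: "After pretests, the children were matched age, sex, and level of functioning and then randomized into the 3 groups". The schedule there is: "This study includes 3 pretests, 3 posttests, and 16 training sessions conducted over 10 weeks. Eight weeks later a follow-up test was also completed".

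The only rule on non-completion is an eligibility criterion for children who "could not complete the pretests due to behavioral issues". It acts before randomisation and does not cover later losses. Neither document defines an analysis population, says that children are analysed in the arm allocated, gives a method for missing scores, or says whether a child who stops training is still tested.

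**The concern.** A paired or change-score t-test needs both scores from each child, and so does a classical repeated measures ANOVA. A child with a pretest but no posttest contributes nothing, even if a follow-up score exists, because the SAP does not use the follow-up.

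The arms ask different things of the child: synchronised whole-body movement to music, exercise and games, or seated reading and fine motor work. Training is 16 sessions of about an hour over 8 weeks, under pandemic restrictions. It is plausible that loss could depend on both arm and level of functioning, although nothing shows that it did.

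If it does, the remaining children in one arm start from a higher pretest than those in the other. Change scores do not neutralise that difference. Children with higher pretests tend to show less change through regression to the mean, so the contrast in change is no longer zero when training has no effect. The balance sought by matching and randomisation is lost, and the planned analysis has no term to restore it.

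**Working it through.** The documents give no power, alpha, SD, effect size or dropout figure, so there is no stated number to reproduce. What follows is an illustration.

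**Inputs.** From the documents: 45 children and 3 arms. Assumed: equal allocation (45 / 3 = 15 per arm), no true effect, normal scores with equal pre and post SD, pre-post correlation r of 0.5, 0.7 or 0.9, two-sided alpha of 0.05, and 3 of 15 (20%) or 5 of 15 (33%) children lost from one arm only, always those with the lowest pretests.

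**Equivalence of the methods.** With two occasions, the arm-by-time test in a repeated measures ANOVA is the test of equal mean change between arms. The t-test and ANOVA options therefore share the same bias. A standard repeated measures ANOVA routine, given data with one posttest removed, rejected them as unbalanced.

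**Bias.** For a child whose pretest lies x SD from the mean,

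expected change = r·x − x = −(1 − r)·x.

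The bias in the depleted arm is −(1 − r) times the mean x of those who remain. For standard normal scores, the expected mean of the highest 12 of 15 is 0.327, and of the highest 10 of 15 is 0.516.

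| Lost from one arm | r | Formula | Simulated bias in change (SD) | Simulated type I error |
|---|---|---|---|---|
| 3 of 15 | 0.5 | −0.5 × 0.327 = −0.164 | −0.163 | about 7% |
| 3 of 15 | 0.7 | −0.3 × 0.327 = −0.098 | −0.097 | about 6% |
| 3 of 15 | 0.9 | −0.1 × 0.327 = −0.033 | −0.031 | about 5% |
| 5 of 15 | 0.5 | −0.5 × 0.516 = −0.258 | −0.257 | about 10% |
| 5 of 15 | 0.7 | −0.3 × 0.516 = −0.155 | −0.156 | about 8% |
| 5 of 15 | 0.9 | −0.1 × 0.516 = −0.052 | −0.051 | about 6% |

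The minus sign means that the arm with losses shows a falsely smaller gain. If that is the multimodal arm, its advantage is understated; if it is the control arm, the advantage is overstated. For praxis errors, where a high count is poor, losing the poorest performers again makes that arm's improvement look smaller.

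**Same children, pretest as covariate.** With the same children still missing, regressing the posttest on arm and pretest gave a bias of at most 0.006 SD in all six settings, and type I error of about 5%.

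**Other patterns of loss.**
- Both arms lose their 3 or 5 lowest-pretest children: bias in the change contrast is at most 0.004 SD.
- Random loss: type I error stays near 5% and only precision suffers. The detectable difference at 80% power, in SD of the change score, is (1.960 + 0.842) × √(2/n). That is 1.02 at n = 15 and 1.14 at n = 12.
- The 3 lowest changers are lost from one arm: bias is 0.33 SD of the change score, in that arm's favour, and type I error is 15.6%. This loss depends on the unseen outcome, and conditioning on the pretest does not correct it.

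**The case against.** The strongest reply is that the figures do not show harm from dropping children as such. The same children are missing from the pretest-adjusted analysis, and the bias is gone. This stands: what the figures price is the unadjusted change score under selective loss. They show no separate gain from a mixed model or from bringing children back for testing.

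The scenario is also severe, and its effect is modest. All losses fall in one arm and always at the bottom of the pretest range. With 3 lost, the biases of 0.16, 0.10 and 0.03 SD compare with standard errors of about 0.38, 0.30 and 0.17. That too stands, and it is why the error rates are given beside the biases.

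A reader might infer more than the documents support:
- **That the SAP orders exclusion of children without a posttest.** It does not. The deletion follows from the methods named.
- **That the arm results become results for children who completed training.** The protocol's posttests are tied to the study calendar, not to sessions attended. A child who stops training but attends the posttest is analysed under the planned methods. The analysed set is children with a posttest; how far that coincides with training completers is left open.
- **That attrition occurred.** No passage reports any. The protocol speaks of the follow-up as completed, and families could choose face-to-face or telehealth delivery, which may have limited loss. Neither point proves full retention.

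Finally, the protocol describes conduct in the past tense, with the study placed between 2019 and 2022. A retention rule may come too late for these children. The analysis can still be changed.

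**Conclusion.** The point holds as a weakness in the choice of analysis. The planned methods are complete-pair methods without pretest conditioning, no as-allocated rule is stated, the follow-up is unused, and nothing elsewhere in either document repairs this.

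On the assumptions above, the false difference runs from 0.03 to 0.16 SD with 3 of 15 lost and from 0.05 to 0.26 SD with 5 of 15 lost, always against the arm with the losses. Type I error rises to between about 5% and 10%. The loss rates, the one-arm pattern, the correlations and the 15 per arm are all assumed. If every child had a posttest this bias is absent; if loss was random the cost is precision alone. The change is worth making because it is cheap and protects against a pattern that the plan cannot rule out, not because bias has been shown.

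**What to change.** In the SAP, replace the t-test or repeated measures ANOVA with a pretest-conditioned comparison of all randomised children in the arm allocated. Either of these would serve:
- a mixed model for repeated measures with a common pretest mean across arms, using every available pretest, posttest and follow-up score, with the posttest contrast between arms as the target; or
- an ANCOVA of the posttest with the pretest as covariate. This is simpler, but it still uses only children with a posttest.

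The mixed model also uses partial records, under the assumption that loss depends only on observed scores. Neither option corrects loss driven by the unobserved change itself.

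Report the number of children without a posttest by arm, and give the complete-pair analysis as a sensitivity analysis. Where testing is still open, state under Experimental Procedures that a child who stops training remains invited to the scheduled posttest and follow-up.

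The cost is a few sentences and slightly more analysis work on scores already scheduled. Where testing is open, there is also the effort of bringing back children who stopped. The estimate may move in either direction.
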